Both differences will be tabulated by study group, over the successive periods between the scheduled visits of the patient at the investigational centre previously defined, separately and globally, using quantitative descriptive statistics. These tabulations, as well as their graphical representations and analyses over time described below will be performed twice in the subgroup of patients on oxygen therapy at any time throughout their study participation and on the period of their oxygen prescription overlapping their holding of the *NOWOX* device: first, on all recordings collected by the *NOWOX* device for all patients constituting the ITT data set, and second, on the recordings collected on the days when patients from the ITT data set are not on any concomitant respiratory assistance (*i.e., Continuous Positive Airway Pressure (CPAP) therapy and/or home Non-Invasive Ventilation (NIV)*) as reported by the investigators. They will be repeated in a second step in the subgroup of patients on continuous LTOT (*i.e., with daily oxygen duration prescribed of 15 hours or more*) at any time throughout their study participation and on the period of their LTOT prescription overlapping their holding of the *NOWOX* device.

Arithmetic means of both average differences separately and their 95.0% confidence intervals will be represented graphically (*the x-axis being the period-axis and the y-axis being the arithmetic mean-axis*) with both study groups being represented separately on the same graph. Moreover, in each study group separately, individual average relative differences will be plotted by corresponding individual daily duration of oxygen prescribed. The same graph will be produced for individual average absolute differences. If a linear or a quadratic trend can be foreseen in any study group, appropriate regression models may be evaluated to assess statistically the trend observed.

Moreover, for each average difference, separate global parametric analyses of variance on repeated measurements will be performed using the same model as the one previously described for the average daily use of oxygen therapy.

**Respiration rate evaluated by the *NOWOX* device:** the average daily respiration rate and the average daily peak respiration rate will be calculated separately over the same periods and in the same way as the average daily use of oxygen therapy. Both estimations of the respiration rate will then be tabulated, analysed and represented graphically in exactly the same way as the average daily use of oxygen therapy previously described (*except its last part related to the relative and absolute individual differences between the *NOWOX* estimations and the actual prescriptions of oxygen therapy*).

**Changes in smoking status:** from Visit 1 onwards, the number and percentage of patients who are current smokers and the number and percentage of patients who are ex-smokers will be tabulated by study group and visit. The corresponding histogram will also be produced.

Moreover, from Visit 1 onwards, a shift table will be provided by study group and visit to depict the number and percentage of patients with the four (4) possible categories of smoking status evolution since their Selection (*Visit 0*):

- number and percentage of patients ex-smokers at Visit 0 and ex-smokers at the post-Run-In tabulated visit,
- number and percentage of patients current smokers at Visit 0 and current smokers at the post-Run-In tabulated visit,
- number and percentage of patients ex-smokers at Visit 0 and current smokers at the post-Run-In tabulated visit,
- number and percentage of patients current smokers at Visit 0 and ex-smokers at the post-Run-In tabulated visit.

At each visit separately, the smoking status evolution since Visit 0 will be compared between both study groups using either the Pearson's Chi-Square test or the Fisher's exact test depending on their distribution.

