### 6.A EFFICACY EVALUATIONS

#### 6.A.1 *Primary efficacy criterion*

The primary efficacy criterion is the **number of unscheduled hospital days, whatever the reason, during the *Follow-Up Period*** for each randomised patient.

Hospitalisations are defined as stays in the following facilities:

- Emergency room, if duration of stay is > 24 hours,
- Intensive care unit, intermediate care unit, surgical or medical wards,
- Nursing facilities following an acute hospital stay.

Scheduled inpatient rehabilitation will not be considered as hospitalisations.

The number of unscheduled hospital days will be calculated for each randomised patient based on the following information recorded by the investigators in the e-CRF for each hospitalisation separately during the *Follow-Up Period*:

- Reason for admission,
- Type of facility,
- Dates of admission and discharge for each facility.

These data will be normalised by total number of days that the patient will have participated in the *Follow-Up Period* to yield the duration of hospitalisations per year, as detailed in section 7.B.3.5.

Each hospitalisation will also be reported as a Serious Adverse Event as defined in section 8.A.

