## **6.C MEDICO-ECONOMIC EVALUATIONS**

### **6.C.1 Costs estimation**

Overall costs will be estimated for each randomised patient from the perspective of the health care payer (*i.e.*, the National Health System in force in the country, with the latest version of the corresponding national tariffs system and reimbursement schedule available at the end of the study). The unit will be the patient. Only health care direct costs will be considered, neither the costs to the family nor the costs to the society will be estimated.

Overall resources used for the patient's medical management (*collected in volume, i.e., by type and/or unit of time, before being priced according to the national tariffs system in force*) will be recorded prospectively alongside the study by the study personnel, as the data used to estimate the overall costs from the perspective of the health care payer for each randomised patient have four (4) components which are part of the clinical parameters recorded, including:

- For each unscheduled hospitalisation (*including home hospitalisations*): the dates of admission and discharge, the type of facility, the primary and secondary diagnoses (*as mentioned in section 6.A.1*), as well as the additional expensive medical procedures and acts performed during hospitalisation, if relevant (*including laboratory and other diagnosis examinations*), and the specific expensive treatments administered or technical devices and equipments used during hospitalisation, whenever possible,
- For each health care consultation: the date, the location, the category of health care provider consulted and the reason for consulting (*as detailed in section 6.A.2.3*),
- For the patients in the Intervention group and for each unscheduled phone call to the health counsellor (*on patient's request or because of symptom scoring*): the date, the reason for calling, as well as the duration of the phone call and associated procedures set up by the health counsellor, and duration of the investigator actions in case of confirmed alarm status (*as mentioned in section 6.A.2.3*),
- For the patients in the Intervention group and for each scheduled education session: the date and duration of the education session performed, its type and location.

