### **PRIMARY ANALYSIS OF THE PRIMARY EFFICACY CRITERION**

The primary analysis of the primary efficacy criterion will correspond to the primary objective of the study, which is to evaluate a strategy of COPD management to reduce the average yearly duration of unscheduled hospitalisations whatever their reason, in patients with GOLD III/IV COPD.

In order to deal with patients followed-up over different duration, their individual recorded cumulated number of unscheduled hospital days whatever their reason ( $D_i$  expressed in days, as recorded by the investigators) will be normalised on a yearly basis, by multiplying  $D_i$  by the ratio [365 days / total number of days of the patient's *Follow-Up Period*] and rounding it at the nearest integer. Thus, a patient for whom 18 unscheduled hospital days have been recorded over a 6-month (182 days) follow-up prior to study premature withdrawal will be analysed as having experienced a yearly estimated duration of hospitalisation of [18 x (365/182)] ~ 36 days. In the same manner, a patient for whom 18 unscheduled hospital days have been recorded over a 2-year (731 days) follow-up will be analysed as having experienced a yearly estimated duration of hospitalisation of [18 x (365/731)] ~ 9 days.

On the ITT data set (*defined in section 7.B.3.1*), the normalised individual yearly duration of unscheduled hospitalisations whatever their reason will be considered as categorical data (0, 1, 2, 3, 4, ... days) and compared between the 2 study groups using the Wilcoxon's rank sum test, in all investigational centres and countries pooled together.

This non-parametric test is commonly used to test that the multinomial distributions of an ordinal categorical parameter are the same across 2 independent samples.

The null hypothesis of interest  $H_0$  is that the distribution of the normalised individual yearly duration of unscheduled hospitalisations whatever their reason in the Intervention group is equal to the one observed in the Control group. The alternative 2-sided hypothesis  $H_1$  is that the distribution of the normalised individual yearly duration of unscheduled hospitalisations whatever their reason in the Intervention group is different from the one observed in the Control group.

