## **ANALYSES OF THE SECONDARY EFFICACY CRITERIA**

All analyses of the secondary efficacy criteria will be performed on the ITT data set (*defined in section 7.B.3.1*).

**The number of hospital days due to severe COPD exacerbations** will be analysed in exactly the same way as the primary efficacy criterion, including its primary, supportive and additional analyses previously described.

**The number of moderate and severe COPD exacerbations** separately as recorded by the investigators will be compared between both study groups with the Wilcoxon's rank sum test, in all countries pooled together.

**Time to first severe COPD exacerbation** (*expressed in number of days*) throughout the *Follow-Up Period* will be tabulated by study group, as quantitative data, in the subgroup of patients from the ITT data set experiencing at least one severe COPD exacerbation during their *Follow-Up Period*, as reported by the investigators, in all countries pooled together. Moreover, time to first severe COPD exacerbation throughout the *Follow-Up Period* will be described globally by study group, on the ITT data set, using Kaplan-Meier's estimates to display the probability of survival and of experiencing severe COPD exacerbation. Survival times will be censored at the earliest time of occurrence of the following events:

- the patients' last contact (*this will apply to the subgroup of patients who never experience any severe COPD exacerbation and who are never hospitalised for any reason during their Follow-Up Period*),
- the time to first severe COPD exacerbation (*for the subgroup of patients experiencing at least one severe COPD exacerbation during their Follow-Up Period*),
- the time to first hospital admission for another reason than COPD exacerbation (*for the subgroup of patients hospitalised at least once during their Follow-Up Period*),
- the time to death for another reason than COPD exacerbation, if applicable.

If relevant, time to first severe COPD exacerbation will be compared between both study groups with the Log rank test.

**The use of health care services due to COPD and to all causes** separately will be tabulated by study group and type or unit of time (*i.e., qualitatively in terms of volume without being priced*). Each category separately will be compared between both study groups using either the Student's t test or the Wilcoxon's rank sum test depending on their distribution.

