In the subgroup of patients on oxygen therapy at Selection and/or during their study participation and on the period of their oxygen prescription overlapping their holding of the *NOWOX* device, the average daily duration prescribed will be tabulated by study group. For each patient for whom a change in the daily duration of oxygen prescription is recorded throughout the *Follow-Up Period*, the individual daily duration of oxygen prescription will be estimated by using the sum of all recorded daily durations prescribed multiplied by the number of days of the corresponding prescription, divided by the total number of days on oxygen therapy. In case of missing or incomplete information necessitating monthly approximation in this average calculation, it will be considered that each month lasts 30.5 days.

**Compliance to oxygen therapy:** in the subgroup of patients on oxygen therapy at Selection and/or during their study participation and on the period of their oxygen prescription overlapping their holding of the *NOWOX* device, the average daily use of oxygen therapy over 24 hours, as well as the average use of oxygen therapy at night (*i.e., over the time interval [22:00 ; 6:00]*) and the average use of oxygen therapy during the day (*i.e., over the time interval [06:00 ; 22:00]*) will be calculated separately over at most eight (8) successive periods (*for the first patients included in the study who have been followed up 24 months*) defined by the scheduled visits of the patients at the investigational centre, without taking into account the recordings collected by the *NOWOX* device on the day of each actual visit, *i.e.,* when applicable, over the successive periods:

- between the day following the actual date of Visit 1 and the day preceding the actual date of Visit 2 (*both included*) (*period 1*),
- between the day following the actual date of Visit 2 and the day preceding the actual date of Visit 3 (*both included*) (*period 2*),
- ... and so on, up to the last period between the day following the actual date of Visit 8 and the day preceding the actual date of Visit 9 (*both included*) (*period 8, if applicable*).

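### Exacerbation counts, and probably health care volumes, are compared without allowing for follow-up time, so unequal dropout or mortality between arms would read as an effect

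*Protocol*

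**What the plan says.** - **Exacerbations (protocol 7.B.3.5, secondary efficacy criteria).** On the numbers of moderate and of severe episodes the text reads "separately as recorded by the investigators will be compared between both study groups with the" and names the Wilcoxon rank sum test, with all countries pooled. No adjustment for time observed is stated, and section 6.A.2.2 defines the criterion as a number of episodes.
- **Health care use (same section).** Volumes are tabulated by type or unit of time. Then: "Each category separately will be compared between both study groups using either the" (t test or Wilcoxon, according to the distribution).
- **Meaning of unit of time (6.C.1).** Resources are collected in volume, "by type and/or unit of time, before being priced according to the national tariffs system in force". Here the phrase describes the unit in which a resource is counted, not a rate per time followed.
- **Primary criterion (6.A.1 and 7.B.3.5).** Hospital days are handled differently: "These data will be normalised by total number of days that the patient will have participated in the" follow-up period. The reason is given in 7.B.3.5: "In order to deal with patients followed-up over different duration, their individual recorded cumulated number of unscheduled hospital days" are multiplied by 365 over days followed. Hospital days due to severe exacerbations follow the same method.
- **Costs (7.B.3.6)** are expressed per month.
- **Length of follow-up.** Section 4.B.3.2 plans 12 months for every patient. Section 7.B.3.5 refers to a period "for the first patients included in the study who have been followed up 24 months", and 7.B.3.7 also refers to Month 24 and Visit 9 for the first patients. Section 7.B.2 expects 25% dropout per year, and 3.D lists death as a reason for withdrawal.
- **Status (7.B).** All results other than the primary analysis are exploratory and descriptive, tested at two-sided 5% without multiplicity adjustment.

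**The concern.** A raw count measures both how often events occur and how long the patient was watched. The ITT set includes everyone who enters follow-up, so a patient who dies or leaves in the second week ranks among those with few exacerbations. If one arm loses more patients, or loses them earlier, its counts fall for that reason alone. The protocol recognises the problem for hospital days and then does not carry the remedy to the counts in the next paragraph.

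The route to a difference between arms is plausible, though not predicted. The trial is open. Section 3.D gives the Intervention group extra criteria for stopping the allocated strategy, and 4.B.5 allows withdrawal at the investigator's discretion. What is at stake is the reading of the exacerbation results. Section 1.C expects the programme to make severe exacerbations less frequent. Frequency is a rate, and a Wilcoxon p-value on counts does not estimate one.

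**Working it through.** **1. The plan's own figures.** The protocol gives no figure for the secondary counts. Its normalisation examples reproduce: 18 × 365/182 = 36.1 and 18 × 365/731 = 9.0 days. The sample size is also consistent: 143/(1 − 0.0625) = 152.5, so 153 per arm, which is used below.

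**2. Mean follow-up over a 12-month plan.** With yearly dropout p and a constant hazard, mean follow-up in years is p / (−ln(1 − p)).

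| Yearly dropout | Mean follow-up (years) |
|---|---|
| 25% (protocol) | 0.25/0.2877 = 0.869 |
| 10% (assumed) | 0.10/0.1054 = 0.949 |
| 35% (assumed) | 0.35/0.4308 = 0.812 |
| 15% (assumed) | 0.15/0.1625 = 0.923 |

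With the same true rate in both arms, the ratio of mean counts equals the ratio of mean follow-up:
- 25% v 10%: 0.869/0.949 = 0.916, a mean count 8.4% lower in the arm that loses more.
- 35% v 15%: 0.812/0.923 = 0.880, 12% lower.
- 25% v 25%: ratio 1, no difference.

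At the same rate, a patient followed for 24 months has 2.0 times the expected count of one followed for 12. That compares patients, not arms.

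**3. Effect on the planned rank test.** Because the exacerbation test is a Wilcoxon, its false-positive rate was simulated with identical true rates, 153 per arm and two-sided 5%. Assumptions not in the documents: 1.0 or 2.5 events per year, gamma-Poisson counts with dispersion 0.7, exponential dropout unrelated to a patient's event rate, and 0% or 20% of patients on a 24-month schedule. Ranges cover these settings.

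| Dropout, arm v arm | Wilcoxon, raw counts | Wilcoxon, counts scaled to 365 days |
|---|---|---|
| 25% v 25% | 4-5% | 4-5% |
| 30% v 20% | 8-11% | 5-7% |
| 35% v 15% | 14-26% | 8-9% |
| 40% v 10% | 25-53% | 12-14% |

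A rate ratio with follow-up as offset and a robust standard error gave 5.0-5.9% across all the scenarios.

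Where dropout was unequal, most false positives favoured the arm with less follow-up: at least 87% of them at 30% v 20%, and about 98% or more at 35% v 15%. For example, at 2.5 events per year, 35% v 15% dropout and 20% of patients on 24 months, mean counts were 2.29 v 2.70 with no true difference.

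**4. What the table shows.** The raw-count test is valid when follow-up is equally distributed, including when some patients have 24 months. It fails as the arms diverge. Copying the primary criterion's scaling reduces the inflation but does not remove it; the offset model does, under these assumptions.

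**The case against.** The strongest reply is that the harm is conditional. Section 7.B.2 gives one dropout rate for both groups, and nothing in the protocol predicts a difference. At 25% in both arms there is no inflation. This stands.

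Other points also carry weight:
- **24-month patients.** A reader might infer that they bias the comparison. Allocation is randomised within centre (4.B.2), so they should be roughly balanced and mainly add noise. The documents do not say how many there are.
- **Discontinuation rules.** A reader might infer that the extra Intervention-group criteria shorten that arm's follow-up. Section 3.D keeps such patients in follow-up to Month 12 whenever possible, so this need not happen.
- **Visibility.** Section 7.B.3.3 compares time to dropout by log-rank test, and time to death if relevant; 7.B.3.7 tabulates follow-up duration by group. An imbalance would be seen, but seeing it does not correct the count comparison.
- **Related analyses.** Severe exacerbations also have scaled hospital days and a Kaplan-Meier analysis of time to first event, and costs are monthly. The moderate count and the recurrent severe count have no comparable analysis.
- **Health care wording.** It is less explicit than the exacerbation wording. Section 6.C.1 supports reading it as unscaled volume, but this part is a probable reading, not a certain one.
- **Source of the data.** The reference to what investigators recorded identifies the data source and does not by itself mean unscaled. The point rests on the absence of any scaling.

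This is not a detail merely left for the SAP: the protocol names both the quantity and the test.

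**Conclusion.** The point holds in conditional form. The protocol fixes a comparison of exacerbation numbers, and probably of health care volumes, that ignores follow-up time, while correcting the neighbouring criterion for that reason. With equal follow-up the test keeps its level. With unequal dropout or mortality the arm observed for less time looks better: 8-11% false positives at 30% v 20% dropout and 14-26% at 35% v 15%. These sizes rest on assumed dropout contrasts, event rates and dispersion, none of which is in the documents.

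A reader might go further and conclude that the exacerbation results will be biased, or that the trial's main finding is at risk. The documents support neither. No difference in dropout is predicted, the primary criterion is scaled to follow-up, and section 7.B classes these secondary results as exploratory and bars causal interpretation of them.

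**What to change.** Analyse moderate, severe and total exacerbations, and health care contacts, by negative binomial (or robust Poisson) regression with log(days of follow-up) as offset, and report the rate ratio with 95% CI. Count events and days over the same first 12 months for every patient. Adjust for smoking status and need for respiratory assistance. If a geographic term is wanted, use country: about 45 centres for 306 patients is roughly 7 per centre, too few for individual centre terms in a count model. State explicitly that health care use is analysed per time followed. The Wilcoxon test on counts can stay as a sensitivity analysis.

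The cost is revised wording and slightly more analysis work. Follow-up days are already needed for the primary criterion, so no new data are required. The price is a model assumption. The offset also does not correct for dropout related to a patient's own exacerbation risk, so the planned comparisons of dropout and death should be read alongside the rate ratios.

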#### **4.B.2 Method of assigning patients to study groups**

According to their smoking status, their need for respiratory assistance (*i.e., home oxygen therapy or Non-Invasive Ventilation*) for chronic respiratory failure at Selection and their investigational centre, included patients will be randomly assigned to either the Intervention group or the Control group, according to a computer generated randomisation list pre-specified prior to the study start. The randomly allocated study group to a given included patient and the corresponding 4-digit randomisation number will be attributed in sequential numerical order by the study dedicated telephone Interactive Voice Response System (IVRS). This randomisation number will be used throughout the study as the identification number for all randomised patients.

The randomly allocated study group and the corresponding 4-digit randomisation number will be notified to the investigator through the IVRS and they will be confirmed automatically *via* an e-mail and/or fax sent to the investigator. The investigator will print the randomisation confirmation e-mail/fax and file it in the investigator binder.

Neither the patient nor the study personnel of the investigational centre will be blinded as to the study group allocated, after randomisation.

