#### 6.A.2 *Secondary efficacy criteria*

##### 6.A.2.1. Number of hospital days due to severe COPD exacerbation

On the basis of the reasons for admission of each hospitalisation during the *Follow-Up Period*, as reported by the investigators in the e-CRF, the number of hospital days due to severe COPD exacerbation will also be calculated for each randomised patient.

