## **6.D ENDPOINT VALIDATION COMMITTEE**

An Endpoint Validation Committee (EVC) will be established to review in a blind manner all hospitalisations having been reported for each randomised patient during the *Follow-Up Period*. The major reason is that hospitalisation may be considered as a potentially biased outcome measure, because somewhat subjective, and physician- or centre-dependent, as health care availability, each physician's routine practice and social considerations can markedly influence the decision to hospitalise a patient.

The EVC will be composed of three (3) independent physicians with clinical and research expertise in COPD. The 3 members will be appointed by the sponsor (AIR LIQUIDE Santé INTERNATIONAL) but will not be involved in the study conduct.

The role of the EVC members will be to adjudicate the reason and appropriateness of all hospital admissions and, for hospitalisations due to COPD exacerbation, to check for the presence of recognised criteria for hospital admission as published in the GOLD 2008 guidelines. Adjudication rules will be defined by the EVC members and sponsor representatives before starting adjudication of cases.

To adjudicate all hospitalisations recorded, the EVC members will review all individual medical reports (*anonymous reports, blinded for study group allocation, and translated in English by the study Clinical Research Associates (CRAs)*) related to hospitalisations having occurred in randomised patients during the *Follow-Up Period*. The following will be adjudicated:

- Criteria for hospitalisation,
- Reason for hospitalisation: first attributing the hospitalisation to a specific cause, then distinguishing hospitalisations directly related to COPD and to other causes, then grouping them into general pathophysiological categories (*respiratory, cardiovascular, cancer or other*),
- Cause of prolonged hospitalisation (*defined by an overall duration of hospitalisation > 30 days*).

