Each EVC member will independently analyse, by batches of 50 cases, all hospitalisation reports and will provide the sponsor with a written signed adjudication form for each of them. Cases will be considered as resolved if the 3 members agreed on adjudication parameters. Regular telephone meetings will take place during the study and will be organised to discuss only the reports not unanimously adjudicated in order to further review (*additional medical information could be requested to the investigational centre*) and discuss the case until complete consensus is achieved. Consensus will be written into a final dated and signed adjudication form. All forms and subsequent analyses will be used by the sponsor as supportive information to discuss and interpret the study results. Indeed, whatever the conclusions of the EVC members on the definition of the primary efficacy criterion, the information recorded by the investigators will be used for the primary analysis of the primary efficacy criterion.

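### Number of severe COPD exacerbations and time to the first one rest only on the unblinded investigator's attribution, although a blinded committee adjudicates the cause of every Follow-Up admission

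*Protocol*

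**What the plan says.** **Source of the two endpoints.** Protocol section 6.A.2.2 has investigators record each exacerbation and defines a severe one by hospitalisation and/or death. In section 7.B.3.5 the moderate and severe counts "separately as recorded by the investigators will be compared between both study groups" by the Wilcoxon rank sum test. Time to first severe exacerbation is tabulated for patients with such an event "as reported by the investigators, in all countries pooled together". It is also described by Kaplan-Meier estimates, with a log-rank test if relevant. One censoring time in that analysis is "the time to first hospital admission for another reason than COPD exacerbation".

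**Blinding.** Section 4.B.2 states: "Neither the patient nor the study personnel of the investigational centre will be blinded as to the study group allocated, after randomisation".

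**The committee.** Section 6.D sets up three independent physicians who review, without knowledge of the group, all hospitalisations reported in the Follow-Up Period. Their task on cause is "first attributing the hospitalisation to a specific cause, then distinguishing hospitalisations directly related to COPD and to other causes". The stated reason is that hospitalisation is partly subjective and varies by physician and centre. Their output is "used by the sponsor as supportive information to discuss and interpret the study results", and the investigators' record stays the source for the primary analysis of the primary criterion.

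**Where the committee's data are used.** The additional analyses in 7.B.3.5 repeat the primary comparison on EVC-confirmed hospital duration. Hospital days due to severe exacerbations inherit that repeat, because 7.B.3.5 gives them the primary criterion's full set of analyses. No such repeat is written for the count or for time to first event.

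**The concern.** For these two endpoints the cause of an admission decides whether an event exists. An admission filed as pneumonia, cardiac or other is not a severe exacerbation. The person who files it knows the group and, for Intervention patients, receives confirmed alarms and makes the medical decision (Appendix 2). If attribution differed between groups, a difference could appear without any difference in exacerbations.

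The allocation of safeguards is uneven. The all-cause primary criterion, which section 1.B says was chosen to limit subjectivity, gets a blinded repeat. Two endpoints that depend on cause do not. Section 1.C names fewer severe exacerbations as an expected effect of the programme, so readers will look at them.

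**Working it through.** **Step 1: which analyses have a blinded version.**

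| Criterion | Depends on cause? | Source named | EVC-based repeat |
|---|---|---|---|
| Unscheduled hospital days, all causes (primary) | No | Investigator | Yes, 7.B.3.5 additional analyses |
| Hospital days due to severe exacerbations | Yes | Investigator (6.A.2.1) | Yes, by cross-reference in 7.B.3.5 |
| Number of severe exacerbations | Yes | Investigator | None written |
| Time to first severe exacerbation | Yes | Investigator | None written |

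**Step 2: how attribution enters.** In the count, a relabelled admission removes one event. In the time-to-event analysis it acts twice: the event is lost, and the cause-based censoring rule ends that patient's observation on the same date, so a later true exacerbation is not seen either.

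**Step 3: group size.** The protocol gives no figure for these endpoints, so only its sample size can be reproduced (section 7.B.2: difference 10 days, SD 25, two-sided 0.05, power 0.90).
- P = Φ(10 / (25√2)) = 0.6114.
- n = (1.960 + 1.282)² / [6 × (0.6114 − 0.5)²] = 141.2, so 142 per group against 143 stated.
- 143 / (1 − 0.0625) = 152.5, so 153 per group as stated.

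The sample size stands, and 153 per group is used below.

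**Step 4: illustration for the count.** All rates here are assumptions; the documents give neither an event rate nor a misattribution rate. There is no true effect. Severe exacerbations are negative binomial with mean 0.7 to 1.5 per year and variance = mean + k × mean². A share of events is relabelled as another cause in the Intervention group only. Each setting has 2,000 simulated trials and a two-sided 5% Wilcoxon test. The table gives the share of trials significant in favour of the programme.

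| Relabelled, Intervention only | k = 0.5 to 1 | k = 2 |
|---|---|---|
| 0% | 2-3% | 2-3% |
| 10% | 7-12% | 5-7% |
| 20% | 18-35% | 12-17% |

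With 20% relabelled equally in both groups the share is 2-3%, the same as with none.

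**Step 5: cross-check with a different model.** Assume that a proportion p₀ of patients in both arms truly has at least one severe exacerbation, and that a share m of them is relabelled in one arm only, so p₁ = p₀(1 − m). The test is a two-sided 5% comparison of proportions.
- Example, p₀ = 0.5 and m = 0.10: p₁ = 0.45 and the difference is 0.05.
- Null SE = √(2 × 0.475 × 0.525 / 153) = 0.0571; actual SE = √((0.25 + 0.2475) / 153) = 0.0570.
- Rejection rate = Φ((0.05 − 1.96 × 0.0571) / 0.0570) + Φ((−0.05 − 1.96 × 0.0571) / 0.0570) = 0.14.

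Over p₀ = 0.4 to 0.6 the rate is 5% at m = 0, 6.5-8.3% at 5%, 11-19% at 10% and 31-56% at 20%. These count both directions, so they are not on the same scale as Step 4; the pattern agrees.

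**The case against.** **The endpoints are exploratory.** Section 7.B makes everything beyond the primary analysis exploratory and descriptive, without causal interpretation. This stands and limits the weight of the point. The comparisons are still tested at 5%, and a descriptive estimate also benefits from a cause assigned without knowledge of the group.

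**A further repeat could sit in the SAP, which is not at hand.** That is possible, and nothing in 6.D forbids it: the explicit reservation of investigator data covers only the primary analysis of the primary criterion. But the protocol does not leave the source open here. It names the investigators for both endpoints and extends the blinded repeat elsewhere.

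**There are partial safeguards.** Monitors check the e-CRF against source files (9.C), diagnoses are coded for each unscheduled hospitalisation (6.C.1), and the repeat on exacerbation hospital days should reveal gross differences in attribution. These reduce the risk without giving these two endpoints a blinded result.

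**Stronger readings that the documents do not support.**
- A reader might infer that hospital days due to exacerbation have the same gap, since 6.A.2.1 also relies on the investigators' reasons for admission. They do not; the repeat is inherited.
- A reader might infer that bias favours the programme. Direction is unknown: closer surveillance could equally make investigators readier to call an Intervention admission an exacerbation.
- A reader might infer that the investigator runs the alarm system. Appendix 2 has the vocal server score and the health counsellor confirm; the investigator then decides.
- A reader might infer that EVC data remove the bias at no cost. The committee reads hospital reports that may carry the treating team's diagnosis, and it cannot undo an unblinded decision to admit. It does not review moderate exacerbations or deaths without admission.

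**Conclusion.** The point holds for the number of severe exacerbations and the time to the first one, including its cause-based censoring. Both rest only on an unblinded attribution, while a blinded one is already collected for every Follow-Up admission.

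The size is conditional. With assumed means of 0.7 to 1.5 events per year, k of 0.5 to 2, 153 per group and 10% relabelling in the Intervention group only, false findings favouring the programme rise from 2-3% to about 5-12%. Equal relabelling changes nothing. The documents establish the opportunity, not that differential relabelling will occur.

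The primary criterion is all-cause, so its conclusion is unaffected. This is a worthwhile improvement to two exploratory endpoints, not a flaw in the trial's main result.

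**What to change.** In sections 6.A.2.2 and 7.B.3.5:

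- Analyse admission-based severe exacerbations (count, time to first, and censoring at admission for another cause) on the EVC-adjudicated cause alongside the investigator-recorded version. Preferably the EVC version leads; at minimum it is a pre-specified repeat, as for the primary criterion.
- State which adjudicated category counts as a severe exacerbation, and apply the existing 14-day new-episode rule of 6.A.2.2 to the adjudicated events.
- Keep the investigator's cause for deaths without admission and for moderate exacerbations, which the EVC does not review.
- Leave hospital days due to exacerbation and the all-cause primary analysis as they are.

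The cost is wording in two sections, one extra analysis run, and an event definition that draws on two sources and must be described as such. No new data collection is needed, because 6.D already covers all Follow-Up hospitalisations.
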